## 2.7 Protocol Violations

A high rate of protocol violations was seen in previous trials of venous ulceration (including the ESCHAR trial) and this is likely to reflect the reluctance and apprehension of elderly patients to undergo surgical interventions involving general anaesthesia. The treatment of superficial venous disease involves a range of minimally invasive, endovenous modalities that can be performed using local or no anaesthesia. Procedures are performed on an outpatient basis and can be completed in around 30 minutes. Published studies of endovenous interventions have demonstrated excellent patient satisfaction and few treatment refusals. Due to the published evidence and extensive personal experience among the research team, we believe that the rate of participation will be higher and rate of protocol violations will be lower than previous studies.

The following will be recorded as protocol deviations:

- 1) Patients randomised to multilayer compression / stockings plus early venous reflux ablation, who receive endovenous intervention more than two weeks from randomization.
- 2) Patients who are non-compliant with compression bandaging, defined as use <75% of the prescribed duration.
- 3) Patients randomised to compression bandaging alone who undergo endovenous ablation prior to verified healing.

The type and reason of protocol violation will be documented in this study, and the summary of protocol violations will be reported in both arms.

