5.4 FURTHER TREATMENT FOR STANDARD CARE (COMPRESSION ALONE) ARM

Patients randomised to multilayer compression / stockings alone can be offered endovenous treatment of superficial reflux once healing has been confirmed or at 6 month post randomisation (see 4.3.1). Endovenous ablation should be performed as per standard practice in the treating centre and details of this will be recorded. Endovenous intervention may also be offered if there is clinical deterioration in the active leg ulcer and it is clinically felt that the patient may benefit from early intervention. This will be recorded on the electronic case report form.

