7.2 PLANNED ANALYSES

No formal interim analyses are planned. Informal interim analyses will be performed if requested by the Data Monitoring Committee (DMC) but findings will be made available to member of the DMC only. Basic descriptive methods will be used to present the data on study participants, trial conduct, clinical outcomes and safety (in total and for each study group separately). The primary outcome will be time to complete healing. We will test the hypothesis that there is no difference in time to complete healing between the control and intervention groups using a log-rank test

(two-tailed, 5% significance level). Kaplan-Meier survival curves will also be presented and we will perform a subsidiary analysis investigating the effect of study centre, participant age, ulcer size and chronicity on time to complete healing using Cox regression. To adjust for potential surgeon and centre effects, surgeon and centre will be included in the Cox regression analysis as random effects. All analyses will be on an intention-to-treat basis. If there is substantial cross-over, per-protocol analyses may be explored for sensitivity analyses. Safety and tolerability data will be presented by the two arms on an intention-to-treat basis. The statistical analysis plan (SAP) for the original trial (follow up to 1 year) will be finalised prior to the final analysis. An additional SAP for the extension follow-up (up to 5 years) will be finalised before the analysis of extension data.

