## **2.2 Definition of Population for Analysis**

The study population will comprise all participants who were randomised. A secondary per-protocol analysis will also be carried out after excluding patients with protocol violations. For the analysis of ulcer free time, the population for analysis will be patients with complete follow-up data only. This is because ulcer free time to one year depends on the time of primary ulcer healing and duration of recurrent ulcer (for example, patients with ulcer free time of 0 day may have an unhealed primary ulcer at 1 year follow-up, or may have withdrawn from the study after healing at month 1, or may have withdrawn from the study after healing at month 11). By adding this constraint some bias may have been introduced (as the analysis will have been based on complete cases only) but ulcer free time will have only one interpretation. As a

sensitivity analysis, the analysis of ulcer free time will therefore be repeated using all the patients, irrespective of length of follow up. This should give a very conservative estimate of the treatment effect.

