## 5. Sensitivity analysis

As a sensitivity analysis, we will perform a per-protocol analysis by excluding patients with protocol violations. This sensitivity analysis will cover all primary and secondary outcomes. As the per-protocol analysis leads to the optimal effect of EVRA and could bring attrition bias, we will interpret the results of pre-protocol analysis with extreme caution. The surgeon data is collected separately and not included in the InForm database. If the surgeon data can be merged into the main database and, we will carry out another sensitivity analysis by including surgeon as a random effect in the Cox regression analysis for primary outcome.

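### Per-protocol exclusion for ablation before verified healing drops only unhealed standard-arm patients, includes ablation that Protocol 5.4 permits, and leaves the direction stated in SAP 5 unsupported

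*SAP*

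**What the plan says.** Three parts of the plan meet here.

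- **The rule.** SAP 2.2: "A secondary per-protocol analysis will also be carried out after excluding patients with protocol violations". SAP 5 extends it: "This sensitivity analysis will cover all primary and secondary outcomes". Of the result, SAP 5 says that it "leads to the optimal effect of EVRA and could bring attrition bias, we will interpret the results of pre-protocol analysis with extreme caution".
- **The list.** SAP 2.7, headed as violations, lists three deviations; Protocol 7.6 has the same three. Item 1 is early-arm patients "who receive endovenous intervention more than two weeks from randomization". Item 2 is compression used for less than 75% of the prescribed duration. Item 3 is "Patients randomised to compression bandaging alone who undergo endovenous ablation prior to verified healing", with no exception. No other list exists, but neither document says that this one defines the per-protocol exclusions. That link is an inference.
- **The permission.** Protocol 5.4 allows standard-arm patients to be offered ablation "once healing has been confirmed or at 6 month post randomisation". It adds: "Endovenous intervention may also be offered if there is clinical deterioration in the active leg ulcer".

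Protocol 7.2 is more tentative than the SAP: "If there is substantial cross-over, per-protocol analyses may be explored for sensitivity analyses". The primary analysis is ITT in both documents.

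**The concern.** A standard-arm patient who heals before any ablation can never meet item 3. One who stays unhealed can. Excluding on item 3 therefore removes patients because of their outcome, in one arm only, and the standard arm left behind looks better than it was. A control ablated at week 26 would even be removed from the 24-week healing rate, which was settled two weeks before.

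Some of this ablation is care that Protocol 5.4 allows, so the documents disagree on whether it is a deviation at all.

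At stake is the planned robustness check on every outcome. If its result moves with who was ablated and when, agreement or disagreement with ITT says little about robustness. A reader who trusts the direction given in SAP 5 may take an attenuated per-protocol result as evidence against the treatment, or an inflated one as its true ceiling.

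**Working it through.** **Inputs from the documents.** 24-week healing 60% vs 75%; two-sided 5%; 90% power; 10% dropout; 208 per arm with 254 healed ulcers; target 450 (Protocol 7.1, 7.2). Follow-up for healing is censored at one year (SAP 4.9).

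**The plan's own figure.** With exponential healing, HR = ln(0.25)/ln(0.40) = 1.513. Freedman's formula gives (1.96 + 1.2816)² × (2.513/0.513)² ≈ 252.2, so 253 events (254 stated). Mean healing is 67.5%: 253/0.675 = 374.8, and 374.8/0.9 = 416.5 (416 stated). The planned effect is reproduced.

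**Assumptions, because the documents give no uptake or lateness.** Weekly healing rates are λc = −ln(0.40)/24 = 0.0382 and λe = −ln(0.25)/24 = 0.0578. A share f of controls still unhealed at week 26 is ablated and then heals at λe. A share q of early-arm patients is scheduled late, at weeks 2–6, and heals at λc until ablated. Item 2 is not modelled.

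**Step 1: how many controls are exposed to item 3.** Unhealed at week 26: exp(−26 × 0.0382) = 37.1%, about 77 of 208. Protocol 5.4 allows all of them to be offered ablation.

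**Step 2: 24-week healing in the standard arm after exclusion.** The rate becomes 0.60/(1 − 0.371f): 62.3%, 66.1% and 73.6% at f = 10, 25 and 50%. The planned 15-point difference shrinks to 12.7, 8.9 and 1.4 points, although every ablation came after week 24.

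**Step 3: Cox HR to 52 weeks** (simulation, 600,000 per arm; above 1 favours early ablation). Item 1 here assumes that early-arm patients who heal before a late date are not then ablated.

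| Early arm scheduled late | True effect | f = 10% | f = 25% | f = 50% |
|---|---|---|---|---|
| 0% | none: per-protocol | 0.96 | 0.88 | 0.76 |
| 0% | planned: per-protocol (ITT) | 1.45 (1.50) | 1.34 (1.48) | 1.14 (1.44) |
| 20% | planned: per-protocol (ITT) | 1.49 (1.48) | 1.37 (1.46) | 1.17 (1.42) |
| 40% | planned: per-protocol (ITT) | 1.56 (1.46) | 1.44 (1.44) | 1.23 (1.40) |

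So the per-protocol HR can lie below, at or above ITT.

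**Step 4: item 1 alone, no true effect.** The HR is about 1.04 at 20% late and 1.10 at 40% late. If late ablation goes ahead whether or not the ulcer has healed, it is 1.00. With the planned effect and 40% late, that second case gives 1.51 against ITT 1.47: dilution is removed and no bias is added.

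**Step 5: timing of control cross-over.** Suppose 20% of controls are scheduled for ablation regardless of prognosis, and ablated if unhealed. With the planned effect, item 3 exclusion against ITT gives about 1.48 vs 1.41–1.42 at weeks 0–4, and about 1.40 vs 1.44 at weeks 8–12. Both per-protocol values are below the no-deviation 1.51.

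**Step 6: other consequences.** With 225 per arm and no true effect (nominal 2.5% each way), the per-protocol test is significant against early ablation in 21% of trials at 25% uptake with nobody late, and for it in 14% at 40% late with no uptake. For ulcer-free time (no recurrence assumed), the per-protocol difference at 25% uptake and nobody late is 29 days against 41 days for ITT.

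**Step 7: the alternative.** In the same model, censoring at the deviation in both arms gives 1.00 with no true effect and about 1.49–1.52 with the planned effect, at every f and q.

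**The case against.** **ITT is primary, and SAP 5 already warns of attrition bias and urges extreme caution.** Both are true, and they limit the severity. But a general caution does not correct a stated direction that has no reason behind it.

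**The extremes drive the range.** They do. SAP 2.7 expects few violations, Protocol 3.3 excludes patients the centre cannot treat promptly, and SAP 2.6 restricts randomisation to willing patients. At 10% uptake and 0–20% late, the per-protocol HR is 1.45–1.49 against ITT 1.48–1.50, a small difference. The same willingness, however, makes uptake under Protocol 5.4 plausible.

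**Item 3 exclusion can move the HR towards early ablation.** Relative to ITT, yes, when cross-over is early and unrelated to prognosis (step 5). A reader might infer that excluding on item 3 always pulls the result below ITT; that does not hold. What holds is bias against early ablation relative to the HR without deviations.

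**Item 1 need not bias anything.** Correct. Its text does not mention healing, and Protocol 4 and 5.4 treat ablation after healing as ordinary care. A reader might infer that items 1 and 3 select on healing in opposite directions. They do not: both can remove slow healers. Only their effects on the treatment contrast oppose, because they act in different arms, and item 1's effect arises only if healed patients are not ablated late.

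**Planning what Protocol 7.2 says may be explored is not an error.** Agreed; it is fuller prespecification.

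**Censoring is not bias-free.** Also correct. In a gamma-frailty check with no true effect, unweighted censoring gave 0.90–0.98 when the worst 10–50% of unhealed controls were ablated at week 26, and 0.84–0.86 when the worst 13% of controls were ablated at week 8. Whole-patient exclusion in the week-8 case gave 0.78.

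**Conclusion.** The point stands in a limited form. The text alone establishes that item 3 (SAP 2.7, Protocol 7.6) conflicts with Protocol 5.4, and that whole-patient exclusion on item 3 selects on the outcome. The size rests on assumptions about uptake, lateness and exponential healing. Item 3 alone takes a null HR to about 0.96 at 10% uptake and 0.76 at 50%; item 1 can take it to about 1.04–1.10 under its condition, or leave it unchanged.

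The plan does not fix the net direction relative to ITT, so SAP 5's claim of an optimal effect is unsupported. This does not show that the claim would be wrong in every realisation, nor that the primary analysis is biased; the documents support neither reading. This should be fixed before the per-protocol analysis is run, with less confidence about item 1 than about item 3.

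**What to change.** 1. **Reconcile and define.** Settle between Protocol 5.4 and item 3 of SAP 2.7 and Protocol 7.6 whether ablation under 5.4 counts as a violation. State whether the SAP 2.7 list defines the per-protocol exclusions. Reconcile item 2 with Protocol 3.3, which says that a period of compression non-compliance is not a protocol violation.
2. **Time to healing.** Do not exclude whole patients on item 1 or item 3. Keep everyone and censor at the deviation in both arms: the standard arm at pre-healing ablation, the early arm at two weeks if unhealed and not yet ablated (which also covers those never ablated). Weight by inverse probability of censoring, using baseline age, ulcer size, ulcer duration and centre. Add the 6-week tracing only for censoring after week 6. State that informative censoring from deterioration-driven ablation may remain.
3. **Other outcomes.** Where censoring does not apply, as for ulcer-free time, report ITT without item 1 or item 3 exclusions.
4. **SAP 5 wording.** Delete the claim of an optimal effect. Say that the direction of an exclusion analysis relative to ITT is not known in advance. Keep the attrition-bias caution.

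Cost: SAP wording, some programming and a less simple sensitivity analysis. Some information is lost: log-rank power with 225 per arm is about 93% at 40% late, against 99% with no deviations. Protocol 5.4 already has standard-arm ablation recorded. Sample size, patient care and the primary analysis do not change.

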## 2.8 Deviations from the SAP

All deviations from the SAP will be disclosed in the final analysis report. If problems or fundamental issues become apparent in the on-going checking that forms part of the statistical analysis, the trial statistician will raise these with a senior statistician who will consult with the

appropriate individuals. Any such action and subsequent decisions will be documented in the final statistical analysis report.

### **3. Interim Analysis**

No formal interim analyses are planned. Informal interim analyses will be performed if requested by the Data Monitoring Committee (DMC) but findings will be made available to members of the DMC only. Unless advised by the DMC in response to clear evidence of benefit or hazard, the Steering Committee, collaborators, participants and all study staff (except those who provide the confidential analyses to the DMC) will remain blind to the results until the end of the study.

## **4. Analysis Plan**

### **4.1 Recruitment Details**

Details about patient enrolment, follow-up and inclusion in analysis will be provided using a consort diagram (Figure 2).

Recruitment will be summarised by a breakdown of the reasons for exclusion in tabular form.

### **4.2 Baseline Characteristics**

Baseline characteristics, including demographics, medical history, ulcer history, and details of current ulcers will be summarised by treatment group using appropriate descriptive statistics for all randomised participants defined in 2.2 (Table 1, Table 2, Table 3 and Table 4).

### **4.3 Treatment Summary**

Type of endovenous treatment received (Endothermal alone, Foam sclerotherapy alone, Mechanochemical alone (MOCA), Endothermal plus Foam, or MOCA plus Foam) will be summarised by treatment group using appropriate descriptive statistics for all randomised participants defined in 2.2 (Table 5).

### **4.4 Primary Endpoints**

The primary outcome is time to complete healing and we will test the hypothesis that there is no difference in this between the control and intervention groups using a Cox model with study centre as a random effect (Table 6). Kaplan-Meier survival curves and the log-ran test will also be presented (Figure 3). As a subsidiary analysis we will investigate the effect of potential confounders listed in section 2.1 (age, ulcer chronicity and ulcer size) on the treatment effect and on time to complete healing using Cox regression, again with centre included in the Cox regression analysis as random effect (Table 6). To assess whether the treatment effect is consistent across all patient sub-groups, the hazard ratios and 95% confidence intervals for treatment from the above Cox regression models (with adjustment for potential confounders and centre as a random effect) will be re-calculated for each of the following subgroups separately; BMI (<23, 23.0-25.0, 25.01-30.0, > 30), Age ( $\leq 49$ , 50-69, 70+), gender (male, female), smoking (Never, previous, current), ulcer size (by quartile), ulcer duration (by quartile), history of deep vein thrombosis (yes, no), history of rheumatoid arthritis (yes, no), taking anti-platelet therapy (yes, no), history of intervention on previous leg ulcer (yes, no intervention, no previous ulcer) and baseline EQ5D (by quartile). The results will be presented using a Forest plot (Figure 4), with the overall result also included at the bottom. We will also use Cox regression to look for differences between the treatment arms by type of endovenous treatment (Endothermal alone, Foam sclerotherapy alone, Mechanochemical alone (MOCA), Endothermal plus Foam, or MOCA plus Foam). Results (hazard ratios and 95% confidence intervals will also be presented graphically in the Forest plot (Figure 5). These subsidiary analyses are intended to provide reassurance that the observed treatment effect is consistent across all patient sub-groups. The study is not powered to detect differences between sub-groups and any observed patterns should be interpreted extremely cautiously, owing to the smaller numbers and increased chance of Type I error. For Cox regression models the proportionality assumption will be assessed graphically (using diagnostic plots) and using Grambsch and Therneau tests and overall fit will be assessed graphically by plotting the Nelson-Aalen cumulative hazard function versus the Cox-Snell residuals and comparing to a 45°reference line.

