3.2 INCLUSION CRITERIA

- Current leg ulceration of greater than 6 weeks, but less than 6 months duration
- Able to give informed consent to participate in the study after reading the patient information documentation
- Patient age > 18 years
- Ankle Brachial Pressure Index (ABPI) ≥ 0.8
- Superficial venous disease on colour duplex assessment deemed to be significant enough to warrant ablation by the treating clinician (either primary or recurrent venous reflux)

Patients who cannot speak / understand English will be eligible for inclusion and informed consent will be obtained with assistance from translation services as per standard clinical practice. In view of the lack of cross-cultural validation for quality of life tools, only healing outcome data will be collected.

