4.1 PATIENT RANDOMIZATION

The normal clinical team will make initial contact with potentially eligible patients at the referral visit.

Those who consent will be registered on the InForm ITM (Integrated Trial Management) System, a web-based data entry system, which is maintained by ICTU, and their eligibility for the study confirmed. A randomization list will be loaded onto the InForm system for each centre (as stratification will be by centre) before recruitment commences, having been prepared in advance by a statistician who is independent of the study. Each potential participant, if confirmed to be eligible, will be assigned the next available entry in the appropriate randomization list (i.e. without foreknowledge). Thereafter, treatment allocation will not be blinded (with the exception of assessment of ulcer healing – see 4.3.1). For patients with bilateral venous ulceration, the worst leg (according to the patient) will be designated the ‘reference leg’. Interventions may be performed on both legs, if deemed appropriate by the responsible clinician.

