7.1 SAMPLE SIZE CALCULATION

The sample size calculation for this study was based on the primary outcome of ulcer healing. The ESCHAR trial was a similar randomised study, which published the final results in 2007 (see 1.1.3). A total of 500 patients with open or recently healed venous ulcers were randomised to standard therapy alone or standard therapy plus open surgery for superficial venous reflux. The study was powered and designed to evaluate differences in ulcer recurrence (rather than healing).

Consequently, the median time from randomization to treatment delivery was over 7 weeks. Nevertheless, the 24-week healing rate in patients randomised to standard treatment (compression alone) was approximately 60%. Two recent prospective studies evaluating the early treatment of superficial venous reflux suggested that the 24-week healing rate may be as high as 82%^{24 25}.

In order to calculate a sample size for this study, a benefit associated with early treatment is estimated at around 15%. Assuming the 24-week healing rate in the standard arm is 60%, to identify a difference in 24-week healing rates of 15% between the two groups (60% vs 75%) with 90% power and allowing for 10% dropout the study will therefore require 416 subjects (208 in each arm, 254 healed leg ulcers in total). To incorporate further allowances for protocol violations and unexpected dropouts, the target sample size will be 450 patients.

Assuming a 15% drop out rate for the study and that 90% of primary ulcers eventually heal, it is estimated that >340 of the recruited 450 patients will be eligible for inclusion in the ulcer recurrence analysis. With this number of participants, and allowing for the healing rates (of the index ulcer prior to entry into this analysis of ulcer recurrence) to differ by up to 20% between the two study arms, the study extension will have at least 80% power to detect a difference of 15% or more in ulcer recurrence rates between the two arms at the 5% significance level.

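### Protocol 7.2 and SAP 4.4 name different primary tests, and neither uses age, ulcer size and chronicity; making the adjusted Cox model that both already plan the primary analysis would settle both points cheaply

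*SAP*

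**What the plan says.** **Primary test.** Protocol 7.2 compares time to complete healing "between the control and intervention groups using a log-rank test", two-sided at 5%. It does not mention centre for that test, although Protocol 4.1 prepares a separate randomisation list for each centre, "as stratification will be by centre". SAP 2.1 and 4.4 test the same hypothesis "using a Cox model with study centre as a random effect". SAP 4.4 keeps the log-rank test as an additional result.

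**Covariates.** Protocol 6.3 collects age, ulcer duration and ulcer size at baseline. Protocol 7.2 and SAP 4.4 both plan a Cox regression with age, ulcer size and chronicity, and both call it subsidiary. SAP Table 6 prints the centre-only and the multivariate model side by side, each with a hazard ratio and P value, and marks neither column as primary. The subgroup hazard ratios in Figure 4 come from the adjusted model. The overall result at the foot of that figure is not tied to a model.

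**Surgeon.** Protocol 7.2 states that "surgeon and centre will be included in the Cox regression analysis as random effects". SAP 5 explains that surgeon data are held outside the main database and says that, if they can be merged, "we will carry out another sensitivity analysis by including surgeon as a random effect".

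**The concern.** The trial has one confirmatory comparison, and a reader holding both documents finds two names for it. The P value that decides the trial should be identifiable from either document without interpretation.

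The second issue is efficiency. If age, ulcer size and chronicity predict healing, a test that leaves them out has less power than one that includes them. The trial collects them anyway and has already specified the model. What is at stake is a few points of power and a clear statement of which hazard ratio is the headline. The validity of the result is not at stake.

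**Working it through.** **1. The plan's own figure.** Protocol 7.1 sizes the trial "to identify a difference in 24-week healing rates of 15% between the two groups (60% vs 75%) with 90% power", with 10% dropout.

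- HR = ln(1 − 0.75) / ln(1 − 0.60) = 1.513.
- Freedman events = (1.960 + 1.282)² × [(HR + 1)/(HR − 1)]² = 10.507 × 24.00 = 252.2.
- Evaluable patients = 252.2 / 0.675 = 373.6. With dropout, 373.6 / 0.90 = 415.1.

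The protocol states 254 healed ulcers and 416 patients. The sizing is therefore an unadjusted log-rank calculation, reproduced to rounding.

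**2. Power of the present plan.** SAP 4.9 censors at one year, not at 24 weeks. Assuming exponential healing, the proportions healed by 52 weeks are 1 − 0.40^(52/24) = 86.3% and 1 − 0.25^(52/24) = 95.0%, mean 90.7%. Evaluable patients are 416 × 0.9 = 374 or, since "the target sample size will be 450 patients", 450 × 0.9 = 405. Events are then 339 and 367.

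Schoenfeld power = Φ(√events / 2 × ln 1.513 − 1.960):

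- 374 evaluable: Φ(1.85) = 96.8%.
- 405 evaluable: Φ(2.01) = 97.8%.

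**3. Effect of the covariates.** The documents give no prognostic strength, so it is assumed: the SD of the combined covariate index on the log hazard is 0, 0.3, 0.5 or 0.7. Further assumptions are:

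- 20 centres with centre SD 0.3 on the log hazard;
- index variance split 70/20/10% between size, chronicity and age;
- chronicity uniform over 1.5 to 6 months, following the criterion "Current leg ulceration of greater than 6 weeks, but less than 6 months duration";
- group 24-week rates held at 60% and 75% at every SD;
- censoring at 52 weeks, and 2,000 simulated trials per cell (standard error about 0.1 to 0.5 points).

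Power, %:

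| Index SD | Log-rank, 374 | Centre-only Cox, 374 | Adjusted Cox, 374 | Centre-only Cox, 405 | Adjusted Cox, 405 |
|---|---|---|---|---|---|
| 0 | 96.85 | 97.45 | 97.05 | 98.30 | 98.25 |
| 0.3 | 96.10 | 97.15 | 98.15 | 98.25 | 99.00 |
| 0.5 | 96.50 | 97.15 | 98.85 | 97.55 | 99.35 |
| 0.7 | 95.00 | 95.90 | 99.80 | 97.30 | 99.80 |

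Adjusted minus centre-only, in points, is −0.40, 1.00, 1.70 and 3.90 at 374, and −0.05, 0.75, 1.80 and 2.50 at 405. The log-rank and centre-only Cox tests fall on opposite sides of 5% in only 0.7 to 1.6% of trials. If follow-up stopped at 24 weeks (374 evaluable, SD 0.5), power would be 93.65% centre-only and 96.7% adjusted.

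**4. Where the gain comes from.** At 374 evaluable:

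| Index SD | HR centre-only | HR adjusted | (ratio of ln HR)² | (ratio of mean z)² | Implied variance ratio |
|---|---|---|---|---|---|
| 0.3 | 1.54 | 1.59 | 1.15 | 1.10 | 1.05 |
| 0.5 | 1.54 | 1.64 | 1.31 | 1.25 | 1.05 |
| 0.7 | 1.52 | 1.70 | 1.61 | 1.51 | 1.06 |

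The last column is the fourth divided by the fifth. It exceeds 1, so the adjusted variance is slightly larger. A separate simulation without centre effects agrees: the standard error of log HR was 0.1104 unadjusted against 0.1120 adjusted at SD 0.3, and 0.1123 against 0.1147 at SD 0.7. The test is stronger because the conditional HR lies further from 1.

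**5. Type I error.** Under no effect (SD 0.5, 4,000 trials), rejection was 4.5% for log-rank, 4.9% for centre-only Cox and 5.2% for adjusted Cox.

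**6. Missing covariates.** With an assumed 10% missing ulcer size (374 evaluable; SD 0/0.3/0.5/0.7), dropping those patients gives power of 95.4/96.7/98.3/98.8%. Giving missing size its own category keeps 97.0/98.1/98.7/99.4%. At SD 0, dropping patients costs about 2 points against the centre-only test. At SD 0.3 the shortfall (96.7 against 97.15%) is within simulation error.

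**The case against.** The strongest reply is that little is wrong. Protocol 7.2 defers to a SAP finalised before the final analysis, and Protocol 7.4 measures deviations against it. The SAP is unambiguous and reports both tests, which almost always agree. The adjusted model is pre-specified in both documents and Table 6 prints it beside the centre-only result, so no analysis is missing. SAP 5 gives the practical reason for the change on surgeon. The power gain is small, on a base already above 90%, and depends on an assumed prognostic strength. Making the adjusted model primary also makes the headline hazard ratio a conditional one, which is a choice of what to estimate and not free precision.

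Nearly all of this stands, and it limits the weight of the point. It does not remove the mismatch between the documents or the case for a primary test that costs nothing in data.

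A reader might infer more in two ways. One is that leaving out the covariates threatens the power of the trial. If HR 1.513 is treated as conditional on the covariates (416 patients, 10% yearly dropout, no centre effect), power without and with adjustment is 92% and 98% at SD 0.5, and 85% and 97% at SD 0.7. The documents do not support that reading: Protocol 7.1 states 60% and 75% as group rates and gives no hazard ratio. With those rates held in the same simulation, unadjusted power is 97.6% and 96.6%. The other is that adjustment would give a tighter estimate, or the equivalent of more patients. Step 4 shows that the interval for log HR does not narrow.

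**Conclusion.** The point holds at minor to moderate weight. The two documents name different primary tests and give surgeon different roles; both differences are mainly matters of documentation. Neither primary test uses three baseline variables that both documents already place in a subsidiary Cox model. Under the stated group rates the present plan meets its 90% power, and nothing in it produces bias or excess type I error.

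The adjusted model would add about 1 to 4 points of power at 374 evaluable patients and about 1 to 2.5 points at 405, for an assumed index SD of 0.3 to 0.7. If the covariates are not prognostic there is no material gain or loss. These sizes rest on the assumed prognostic strength, its split between covariates, the centre number and spread, and exponential healing. The direction does not depend on the exact values, but the amount does. The benefit should be described as test power for a conditional hazard ratio, not as precision.

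**What to change.** Before the arms are compared:

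- Name one primary analysis in Protocol 7.2 and SAP 2.1 and 4.4: the Table 6 multivariate Cox model, with treatment, age, chronicity and ulcer size in quartiles as fixed effects, centre as a random effect, two-sided 5%. Record the change from the log-rank test.
- Add a rule, blind to arm, that keeps patients with a missing baseline covariate in the model. For example, give missing ulcer size its own category and set missing age or chronicity to the overall mean. This leaves untouched the rule against imputing the endpoint (Protocol 7.3, SAP 2.4).
- Report the centre-only hazard ratio beside the adjusted one. Keep the log-rank test, preferably stratified by centre, and the Kaplan-Meier curves as supportive.
- Label the primary column in Table 6 and use the adjusted model for the overall result in Figure 4. Correct SAP 2.1, which cites Table 9 (quality of life) for the adjusted Cox model.
- Give surgeon the same sensitivity-analysis role in both documents, as in SAP 5.

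The cost is wording in two documents, with no new data or visits. Size in quartiles can stay: the squared z ratios are 1.10/1.25/1.51, against 1.11/1.29/1.58 with log area. The price is a headline hazard ratio that is conditional and somewhat further from 1, with a standard error that rises slightly. If the arms have already been compared, the primary label should not be moved and only the documents should be aligned.
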